### 4 STUDY DESIGN

#### 4.1 OVERALL DESIGN

This is a Pilot study that investigates the CBCT image quality improvement provided by the 2D antiscatter grid technology. The primary objective is to assess the improvement in tissue visualization and CT number accuracy, as measured by objective image quality metrics.

- This is a single arm study, where all participants will be scanned with a CBCT system equipped with 2D antiscatter grid technology, referred to as research CBCT with 2D grid. Each participant will also be scanned with a standard clinical CBCT, which will serve as the baseline, or control. Thus, the image quality improvement in research CBCT with 2D grid will be assessed with respect to standard clinical CBCT without 2D grid.
- We anticipate enrolling a total of 42 participants. Groups (1) and (3) will have, in any combination, the collective total value of 21 participants. Group (2) will have 11

participants and Group (4) will have 10 participants. The groups are described as the following:

**Group (1), Photon therapy patients with treatment sites in abdomen or pelvis:** It is particularly challenging to use CBCT to visualize organ boundaries in the abdomen. Disease sites in the abdomen, e.g. the pancreas and liver, are particularly likely to benefit from “online” adaptive radiation therapy due to the proximity of the gastrointestinal tract to targets (online: plan is modified while the patient is on the treatment couch using volumetric setup images).

**Group (2), Photon therapy patients with treatment sites in prostate or prostate bed:** Due to the large tissue volume in the pelvis, scatter is more pronounced, and tissue visualization is degraded. Since larger patients generate more scatter, the image quality is also patient-size dependent. Hence, we will have two subgroups; subgroup stratification will be based on the patient left-right separation at pelvis level (subgroup 1:  $< 40$  cm, subgroup 2:  $\geq 40$  cm). 5 patients will be enrolled in subgroup 1 and 6 patients will be enrolled in subgroup 2. These “small” and “large” pelvis subgroups will allow evaluation of the effect of patient size on the consistency of organ delineation. The threshold of 40 cm comes from our clinical observations; CBCT images from patients with 40 cm (or more) separation are of noticeably lower quality.

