##### 9.4.6.1 SUB-GROUP ANALYSES

1) Subgroup analyses of image quality metrics will be performed for three anatomical site groups:

- Head and Neck
- Pelvis and abdomen
- Prostate or prostate bed

2) A sub-group analysis of image quality metrics will be performed based on the patient size, as measured by the participant's lateral separation in the imaged volume:

- Lateral separation less than 30 cm
- Lateral separation between 30 and 40 cm
- Lateral separation more than 40 cm

3) Participants in the prostate group will be scanned using two substantially different CBCT systems. To investigate the effect of CBCT system on image quality, the following subgroups will be analyzed separately.

- Prostate and prostate bed subgroup scanned with photon therapy CBCT.
- Prostate and prostate bed subgroup scanned with proton therapy CBCT.

For each subgroup, image quality metrics extracted from CBCT scans with 2D grid and standard clinical CBCT scans will be compared in a pairwise fashion. 95% Confidence Intervals for the image quality metrics (primary objective) will be calculated and reported for each of the subgroups. And the pairwise comparisons between subgroups will be conducted by comparing the 95% Confidence Intervals.

---

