For each participant and CBCT modality an average delineation will be determined using the STAPLE algorithm. This average delineation will be used as the reference delineation to compute four pairwise CIs between the reference and each observer. This pairwise approach to determine the CIs was chosen over the generalized conformity index since it can be used to account for variability among the observers, which in turn will improve our ability to compare the two imaging modalities. A two-way random effects model (random effects for participant and observer) will be carried out for each modality to calculate the ICC and its 95% confidence interval using bootstrapping for absolute agreement. The ICC will be calculated using the form ICC(2,k) so that the results can be generalized to any observer with a similar skill set. If the 95% confidence interval of ICC does not overlap between the two modalities, we will conclude they are significantly different at a 0.05 significant level. We will also examine whether anatomical location impacts performance through subgroup analyses on Groups 1-3.

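### Non-overlap of two separate 95% confidence intervals is labelled a 0.05-level test in the exploratory ICC analysis, which it is not, and the subgroup comparison has no term for whether the grid benefit differs

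*Combined protocol and SAP*

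**What the plan says.** Section 9.4.7 describes an observer study as one of several candidate exploratory analyses, to be selected by the PI once scanning is complete. On the model it says: "A two-way random effects model (random effects for participant and observer) will be carried out for each modality". Each modality therefore gets its own ICC(2,k), with k = 4 observers, and its own bootstrap 95% confidence interval. The decision rule is "If the 95% confidence interval of ICC does not overlap between the two modalities, we will conclude they are significantly different", and the level attached to it is 0.05. Section 9.2 uses the same non-overlap criterion to justify 32 participants in Groups 1–3.

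Section 9.4.6.1 first compares grid and standard scans pairwise within each subgroup. It then reports 95% intervals for the image quality metrics by subgroup and adds that "the pairwise comparisons between subgroups will be conducted by comparing the 95% Confidence Intervals". It names no significance level, no overlap criterion and no interaction term. Section 9.4.2 gives the purpose: to see how anatomical region and patient size affect the difference between the two CBCT types. The primary comparison in that section is a linear mixed model with a random patient effect.

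**The concern.** Two 95% intervals can overlap while the difference between the estimates is clearly significant. Non-overlap is therefore a stricter criterion than a 0.05 test, and it becomes stricter still when the estimates are positively correlated. Section 4.2 places both scans on one participant in order to remove patient-specific variation; two separately computed intervals throw that advantage away. A reported result at the 0.05 level would carry the wrong error rate, and the chance of detecting a real gain in agreement would be lower than it need be.

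The subgroup issue is different. Whether the grid helps more in one region or size class is a question about the difference between differences. Intervals on metric levels answer another question: whether image quality itself differs between subgroups. Sections 2.1, 4.1 and 9.4.1 already expect quality to differ by site, size and CBCT system.

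**Working it through.** **1. The plan's own figure (section 9.2).** Inputs: N = 32; k = 4 observers; standard ICC 0.95, 0.90 and 0.80; increases of 3.5%, 7.7% and 17%, giving research ICCs of 0.983, 0.969 and 0.936. With exact F intervals for the average-measure two-way ICC at N = 32:

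| Standard ICC | Its upper limit | Research ICC | Its lower limit | Smallest N for separation |
|---|---|---|---|---|
| 0.95 | 0.973 | 0.983 | 0.971 | 37 |
| 0.90 | 0.947 | 0.969 | 0.947 | 32 |
| 0.80 | 0.893 | 0.936 | 0.890 | 34 |

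The 0.90 case reproduces 32 exactly and the 0.80 case nearly so. For 0.95, about 3.6% rather than 3.5% is detectable at N = 32. These are expected limits that only just meet. In simulation with bootstrap intervals, the rule declared a difference in about 48–60% of trials at the stated effects.

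**2. Level of the rule.** Intervals fail to overlap when |difference| > 1.96(SE1 + SE2). The level is therefore

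2 × [1 − Φ(1.96(SE1 + SE2) / SE_diff)], with SE_diff = √(SE1² + SE2² − 2ρ·SE1·SE2).

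With equal SEs the critical value is 3.92/√(2(1 − ρ)), where ρ is the correlation between the two ICC *estimates*. The documents do not give ρ, so the values below are assumptions. A direct two-sided 0.05 test has 80% power when the true difference is 1.96 + 0.84 = 2.80 SE_diff; the rule's power there is 1 − Φ(critical value − 2.80).

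| ρ (assumed) | Critical value | True level | Power when a direct test has 80% |
|---|---|---|---|
| 0 | 2.77 | 0.0056 | 51% |
| 0.25 | 3.20 | 0.0014 | 34% |
| 0.5 | 3.92 | 0.00009 | 13% |

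For independent estimates with SE ratios of 2, 3 and 5, the level is 0.0085, 0.013 and 0.021. It stays well below 0.05.

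**3. Simulation of the planned statistic.** ICC(2,4), n = 32, percentile bootstrap over participants, equal true ICCs. The rule rejected in about 1–2% of trials with uncorrelated scans and 0.2–0.3% with correlated scans (patient-level correlation 0.8). That patient-level correlation produced a correlation between ICC estimates of only about 0.3–0.4, so the ρ = 0.5 row is an extreme case.

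**4. Subgroups.** Take Group 2 (11 participants) against Group 4 (10), on the log scale. SDs are assumed: 0.4 between patients and 0.15 within, so the per-scan SD is √(0.16 + 0.0225) = 0.43. Each cell is how often the two subgroups are flagged as different.

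| Scenario | Overlap of grid-scan level intervals | Overlap of intervals of the paired difference | Interaction t-test |
|---|---|---|---|
| No difference | 0.6% | 0.5% | 5.0% |
| Same benefit, levels 0.6 apart | 54% | 0.6% | 5.0% |
| Same grid level, benefit differs by 0.3 | 0.5% | 55% | 87% |

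The second row depends on the assumptions. With levels 0.7 apart and a per-scan SD of 0.45, the level intervals separate in about 66% of trials at 11 versus 10, and in about 70% with 11 in each group.

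**The case against.** The strongest reply concerns scope. The 0.05 overlap rule is written once, for an exploratory analysis that the PI may not select. A reader might infer that the main grid-versus-standard test is compromised. It is not: section 9.4.2 uses a mixed model that respects the pairing. Nor do the documents extend the rule to the secondary endpoint. Section 9.4.3 uses the ICC but states no decision rule.

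On subgroups, the wording asks only that intervals be compared. An overlap test at 0.05 is the natural reading but not a stated one, and the grid effect is assessed within every subgroup. The intervals could also be meant for the paired difference. If so, the comparison would address benefit and would merely be conservative. What stands is that the text as written refers to the metrics and that no interaction term appears.

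Three further inferences go too far. First, section 9.4.7 says when a difference will be concluded; it does not say that overlapping intervals show there is none. Second, the size classes in sections 4.1 and 9.4.6.1 may look contradictory, but the first is a stratum within Group 2 and the second an analysis grouping for all sites. They nest, except for the placing of a separation of exactly 40 cm. Third, a very small level such as 0.00009 depends on an assumed correlation and should not be presented as the trial's error rate.

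**Conclusion.** Wrong as written, with limited reach. The level given for the ICC rule is incorrect. It is 0.56% for independent estimates with equal SEs, up to about 2% with very unequal SEs, about 1–2% in simulation of the planned statistic with uncorrelated scans, and 0.2–0.3% with correlated scans. None of the settings tried reached 5%. The loss of power is certain in direction, but its size rests on a correlation that the documents do not give. The non-overlap criterion also underlies the sample size in section 9.2.

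The subgroup plan does not test its stated aim. Taken literally, it can flag subgroups whose grid benefit is identical (about 54–70% of the time for level differences of 0.6–0.7 log units, under assumed SDs), and it can miss a real difference in benefit. If intervals of the paired difference were intended, its error rate is about 0.5%. The analyses affected are exploratory or subgroup analyses of a pilot, so this should be corrected but does not endanger the primary result.

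**What to change.** 1. **Section 9.4.7.** Resample participants with both scans kept together, and conclude from a 95% confidence interval for the ICC difference (research minus standard). Name a calibrated method, such as BCa or a studentised interval on a transformed ICC, and check its error rate by simulation. A plain percentile interval rejected about 5–10% of the time under the null at n = 32, so it would replace a conservative rule with one that tends to be too liberal. If this is not wanted, delete the claim of a 0.05 level and describe the two intervals without a test.

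2. **Sections 9.4.2 and 9.4.6.1.** Add CBCT type × anatomical site and CBCT type × lateral separation (continuous) to the mixed model and, for Group 2 versus Group 4, CBCT type × system. Equivalently, compare within-patient log differences between subgroups. Report these estimates with 95% intervals and label them exploratory.

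The cost is revised wording, a few model terms and a short simulation; no further participants or scans are needed. The drawback is that interaction estimates will be imprecise in subgroups this small, and the report should say so.

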## 10 SUPPORTING DOCUMENTATION AND OPERATIONAL CONSIDERATIONS

### 10.1 REGULATORY, ETHICAL, AND STUDY OVERSIGHT CONSIDERATIONS

#### 10.1.1 INFORMED CONSENT PROCESS

##### 10.1.1.1 CONSENT/ASSENT AND OTHER INFORMATIONAL DOCUMENTS PROVIDED TO PARTICIPANTS

Consent forms describing in detail the study intervention, study procedures, and risks are given to the participant and written documentation of informed consent is required prior to starting intervention/administering study product.

##### 10.1.1.2 CONSENT PROCEDURES AND DOCUMENTATION

Informed consent process will be initiated prior to the individual's agreeing to participate in the study and continues throughout the individual's study participation. Extensive discussion of the risks and possible benefits of participation will be provided to the participants and their families.

Consent forms will be IRB-approved, and the participant will be asked to read and review the document. The investigator will explain the research study to the participant and answer any questions that may arise. All participants will receive a verbal explanation in terms suited to their comprehension of the purposes, procedures, and potential risks of the study and of their rights as research participants. Participants will have the opportunity to carefully review the written consent form and ask questions prior to signing. The participants will have the opportunity to discuss the study with their surrogates or think about it prior to agreeing to participate. The participant will sign the informed consent document prior to any procedures being done specifically for the study.

The participants may withdraw consent at any time throughout the course of the trial. A copy of the informed consent document will be given to the participants for their records. The rights and welfare of the participants will be protected by emphasizing to them that the quality of their medical care will not be adversely affected if they decline to participate in this study.

The study allows the inclusion of non-English speaking and non-reading participants. Witnesses to these consent processes will be individuals not associated with the trial and will not have a conflict of interest.

---

### **10.1.2 STUDY DISCONTINUATION AND CLOSURE**

This study may be temporarily suspended or prematurely terminated if there is sufficient reasonable cause. Written notification, documenting the reason for study suspension or termination, will be provided by the suspending or terminating party to Sponsor-Investigator. If the study is prematurely terminated or suspended, the Sponsor-Investigator will promptly inform the IRB and will provide the reason(s) for the termination or suspension.

Circumstances that may warrant termination or suspension include, but are not limited to:

- Determination of unexpected, significant, or unacceptable risk to participants.
- Demonstration of efficacy that would warrant stopping.
- Insufficient compliance to protocol requirements.
- Data that are not sufficiently complete and/or evaluable.
- Determination of futility.

Study may resume once concerns about safety, protocol compliance, and data quality are addressed and satisfy the Sponsor, IRB, DSMC, and/or FDA.

---

### **10.1.3 CONFIDENTIALITY AND PRIVACY**

Participant confidentiality is strictly held in trust by the participating investigators, their staff, and the Sponsor-Investigator(s) and their agents. This confidentiality is extended to the clinical information relating to participants. Therefore, the study protocol, documentation, data, and all other information generated will be held in strict confidence. No information concerning the study or the data will be released to any unauthorized third party without prior written approval of the sponsor.

The study Monitor, other authorized representatives of the Sponsor-Investigator, representatives of the IRB, or pharmaceutical company supplying study product may inspect all documents and records required to be maintained by the investigator, including but not limited to, medical records (office, clinic, or hospital) and pharmacy records for the participants in this study. The clinical study site will permit access to such records.

The study participant's contact information will be securely stored at each clinical site for internal use during the study. At the end of the study, all records will continue to be kept in a secure location for as long a period as dictated by local IRB and Institutional regulations.

Study participant research data, which is for purposes of statistical analysis and scientific reporting, will be transmitted to and stored at the University of Colorado Cancer Center. This will not include the participant's contact or identifying information. Rather, individual participants and their

research data will be identified by a unique study identification number. The study data entry and study management systems used by clinical sites and by the University of Colorado Cancer Center research staff will be secured and password protected. At the end of the study, all study databases will be de-identified and archived at the University of Colorado Cancer Center.

---

#### 10.1.4 FUTURE USE OF STORED DATA

- **Intended Use:** Data collected under this protocol may be used to study the tissue visualization and quantitative accuracy of CBCT images. No genetic testing will be performed.
- **Storage:** Data will be stored using codes assigned by the investigators. Data will be kept in password-protected computers. Only Investigators will have access to the data. Clinical data will be entered into REDCap. The data system includes password protection and internal quality checks, such as automatic range checks, to identify data that appear inconsistent, incomplete, or inaccurate.
- **Tracking:** Data will be tracked using a password-protected spreadsheet.
- **Disposition at completion of the study:** Study participants who request destruction of data will be notified of compliance with such request and all supporting details will be maintained for tracking.

Data collected for this study will be analyzed and stored at the University of Colorado Cancer Center. After the study is completed, the de-identified, archived data will be transmitted to and stored at in data servers at the University of Colorado Cancer Center under the supervision of lead PI for use by other researchers including those outside of the study. Permission to transmit data to the University of Colorado Cancer Center and to other researchers will be included in the informed consent.

During the conduct of the study, an individual participant can choose to withdraw consent to have data stored for future research.

When the study is completed, access to study data will be provided through the University of Colorado Cancer Center.

---

#### 10.1.5 SAFETY OVERSIGHT

The Sponsor-Investigator will be responsible for monitoring the trial per the trial monitoring plan, in addition to overseeing the safety and efficacy of the trial including any specimens collected, executing the data and safety monitoring (DSM) plan, and complying with all reporting

requirements to local and federal authorities. This oversight will be accomplished through additional oversight from the Data and Safety Monitoring Committee (DSMC) at the University of Colorado Cancer Center (CU Cancer Center). The DSMC is responsible for ensuring data quality and study participant safety for all clinical studies at the CU Cancer Center, which is the coordinating institution of this trial. A summary of the DSMC's activities is as follows:

- Conduct of internal audits
- Ongoing review of all unanticipated adverse device effects (UADEs), serious adverse events (SAEs), and unanticipated problems (UAPs)
- May submit recommendations for corrective actions to the CU Cancer Center's Executive Committee

Per the CU Cancer Center Institutional DSM Plan, SAEs and UAPs are reported to the DSMC, IRB and the Sponsor\_Investigator per protocol. All SAEs and UAPs including unanticipated adverse device effects are to be reported to the DSMC within 7 (for fatal or life-threatening events) or 15 (non-life-threatening events) calendar days of the sponsor investigator receiving notification of the occurrence.

Each participant's treatment outcomes will be discussed by the PI and site PI and appropriate staff at regularly scheduled meetings. Data regarding the number of participants, adverse device effects, treatment modifications and treatment responses will be discussed and documented in the meeting's minutes.

The Sponsor-Investigator is responsible for organizing and conducting regularly scheduled teleconferences with all participating sites. The Sponsor-Investigator will also be responsible for including data from all of the participating sites to include the minutes from these regularly scheduled teleconferences between the Sponsor-Investigator and the sites within the overall trial's DSM progress report.

The Sponsor-Investigator will provide a DSM progress report to the CU Cancer Center DSMC on a recurring basis (either every six or twelve months based on DSMC vote). The DSM report will include a protocol summary, current enrollment numbers, summary of adverse device effects to include specific unanticipated adverse device effects, SAEs, UAPs and AEs, any treatment modifications, all protocol deviations, and protocol amendments. The DSM progress report submitted to the DSMC will also include, if applicable, the results of any efficacy data analysis conducted. Results and recommendations from the review of this progress report by the DSMC will then be provided to the Sponsor-Investigator in a DSMC review letter. The Sponsor-Investigator is then responsible for ensuring this letter is submitted to the site's IRB of record at the time of IRB continuing review.

---

#### **10.1.6 CLINICAL MONITORING**

Clinical site monitoring will be conducted to ensure that the rights and well-being of human participants are protected, that the reported trial data are accurate, complete, and verifiable, and that the conduct of the trial is in compliance with the currently approved protocol/ amendment(s), with GCP, and with applicable regulatory requirement(s).

Monitoring for this study will be performed by a CU Cancer Center Clinical Monitor in accordance with the clinical monitoring plan (CMP), incorporated herein by reference. The CMP describes in detail who will conduct the monitoring, at what frequency monitoring will be done, at what level of detail monitoring will be performed, and the distribution of the monitoring reports.

---

